13.2 Study population. Study population will be any patient with an infantile or late-infantile/juvenile gangliosidosis disease.

13.3 Sample size. A total of 30 infants or children:

- 5 patients with infantile Tay-Sachs disease
- 5 patients with juvenile Tay-Sachs disease
- 5 patients with infantile Sandhoff disease
- 5 patients with juvenile Sandhoff disease
- 5 patients with infantile GM1 gangliosidosis
- 5 patients with juvenile GM1 gangliosidosis

13.4 Subject recruitment. Subjects will be recruited from the investigators' clinical practice and through the Lysosomal Disease Network. This clinical trial will be posted on ClinicalTrials.gov and this may serve to recruit patients to the study.

13.5 Subject screening. Eligibility will be assessed during a baseline evaluation and will include confirmation of gangliosidosis disease via mutation analysis and tissue (e.g. leukocyte) ascertainment of level of hexosaminidase or β -galactosidase enzyme activity.

13.6 Prior and concomitant therapy. Subjects may have had previous therapies for gangliosidosis. If subjects are taking miglustat and/or pyrimethamine, and/or are on a ketogenic diet at the time of screening, they will be allowed to continue these therapies and will be allowed to participate in the Syner-G study.

13.7 Inclusion criteria. Subjects will be eligible to participate in the study if all of the following criteria are met: 1) confirmed diagnosis of infantile or juvenile GM1 or GM2 gangliosidosis via mutation analysis and tissue enzyme activity analysis (e.g. leukocyte activity of β -hexosaminidase A, including percent activity contributed from both α -subunit and β -subunits) or tissue β -galactosidase enzyme activity; 2) subjects must be age 0 - 17 years at time of enrollment; and 3) subjects and their caregivers must work closely with their University of Minnesota ketogenic diet team, and with their local ketogenic diet team, which must include a ketogenic dietician and a neurologist trained in the ketogenic diet.

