17.0 Study Timetable / Schedule of Events

BL = Baseline, Wk = Week, M = Month, Y = Year

Study Events	Pre-Study	BL	Wk 1	Wk 2	Wk 3	M 1, Wk 4	M 3	M 6	M 9	Y 1 M 12	M 18	Y 2-5 Annual Visits	Y 2-5 Half-Year Time-Point	Every 3 M Throughout this Research Study	Monthly Assessment after the First Year of Study Participation
Determination of leukocyte hexosaminidase activity level for GM ₂ gangliosidosis patients, or β-galactosidase activity level for GM ₁ gangliosidosis patients	X														
Informed Consent		X													
Demographics data collection		X													
Retrospective data collection		X													
Telephone follow-up call: In addition to the timetable shown here, a member of the study staff will contact the parent at least once weekly during the time when the subject is transitioning onto the ketogenic diet, and while the subject is titrating the miglustat dose, and any time the dose is decreased due to adverse events, until symptoms have re-solved. Additionally, while the subject is on a stable (goal) miglustat dose, side effects will be assessed by telephone contact or at clinic visits every 3 months throughout the study period.		X	X	X	X	X	X	X	X	X	X	X	X	X	
Miglustat goal dose = 100 mg 3X daily. Evaluation of dose titration and tolerance of miglustat therapy by tele-phone contact and during clinic visit. After 1 st year, assessments will continue for a minimum of once monthly.			X	X	X	X	X	X	X	X	X	X	X		X
Ketogenic Diet 4:1 Evaluation by ketogenic dietician and neurologist trained in ketogenic diet (a "ketogenic diet team") per institution's clinical program protocol, either at the research site or locally in subject's geographic area. After 1 st year, assessments will continue for a minimum of once monthly.		X	X	X	X	X	X	X	X	X	X	X	X		X
Neuropsychological Testing changes in neuropsychiatric status as assessed by: age-equivalent scores of Bayley Scales of Infant and Toddler Development; and of Vineland Adaptive Behavior Scales		X								X		X			
Neurological evaluation of changes in seizure frequency and severity, and of movement disorders		X								X		X			

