Measurement of subject weight, height, occipital-frontal circumference, comprehensive metabolic panel (including serum creatinine, estimated GFR, and liver function tests), CBC with plate-lets and differential, lipid panel, neurologic exam to assess for peripheral neuropathy, and urine pregnancy test in all post-pubertal females. It is accept-able for this interval safety monitoring to not occur at the primary study site as long as the neurologic exam is performed by an experienced practitioner.		X					X	X	X	X	X	X	X		

Whenever possible, the scheduled assessments/exams will be conducted on all subjects for the duration of the study. However, due to disease progression or concurrent illness, some patients after enrollment may not be able to fulfill the annual visit requirement. If this occurs, a failure to appear for any given annual visit will not make any subject ineligible to continue as a research participant. For research purposes, the rarity of the gangliosidoses dictates that as much data as possible be collected on any given subject.

When any newly-enrolled subject is already using the Syner-G regimen at time of enrollment, for clinical management, the Schedule of Events for that subject will begin with the scheduled time-point that corresponds to the number of weeks or months that subject has been using Syner-G.

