18.0 Data Analysis

18.1 Subject populations for analysis:

- Intention-to-treat Population (ITT): All subjects who initiate any portion of the treatment regimen in association with this study
- Per-protocol Population (PP): Includes all subjects who initiate treatment and are compliant with at least 75% of prescribed drug doses of miglustat, and at least 3:1 ketogenic diet.
- Safety population: All subjects who receive any amount of the combination treatment regimen. Due to the nature of a combination treatment, multiple groups may be identified, should partial adherence be observed.

18.2 Sample size determination. The sample size for the study was determined primarily by feasibility due to the extremely rare nature of the disease. There are two distinct sub-types to be evaluated: infantile and juvenile. Analysis will be based on variability estimates from published natural history studies^{8,11,19} of the infantile form and juvenile form, and correlation between baseline and annual follow-up for up to 4 years.

18.3 Statistical analysis. Descriptive analyses of baseline characteristics and outcomes will include means, standard deviations, medians, and ranges for continuous variables and frequencies for categorical variables. Treatment compliance for each group will also be evaluated. All analyses will be conducted separately for the two disease sub-types – infantile and juvenile – due to the highly heterogeneous patient groups.

The primary analysis for Syner-G treatment regimen will use the intention-to-treat (ITT) population and evaluate overall survival. This will be evaluated based on chronological age at time of death or conclusion of study (whichever occurs first), and compared to available natural history data. Median survival will be compared to previously reported natural history studies of infantile⁹ and juvenile¹¹ forms. Infantile median survival was estimated at 47 months based on data from the National Tay-Sachs and Allied Diseases database for patients born after 2000.⁹ Median survival for the juvenile form was estimated at 14.5 years.¹¹

A secondary endpoint will be the rate of change (i.e., slope) in neurocognitive functioning over the duration of follow-up, compared to available natural history data. This analysis will be conducted separately for each of the two sub-types: infantile and juvenile. The primary

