neurocognitive functioning endpoint for both pediatric groups is age-equivalent scores of the Bayley Scales of Infant and Toddler Development for expressive communication, receptive communication, fine motor skills and gross motor skills. Another primary neurocognitive functioning endpoint for both pediatric groups is age-equivalent scores of the Vineland Adaptive Behavior Scales. Using general estimating equations (GEE) and an exchangeable working correlation structure, variance estimation for confidence intervals and P-values will take into account the possible correlated nature of multiple measurements on the same individual. Supportive analyses will include evaluation using the per-protocol (PP) population.

Safety analyses will be primarily descriptive, reporting the number and percentage of AEs and descriptive summaries. These analyses will use multiple safety populations according to which components of the combination therapy subjects were exposed to. Due to the longitudinal nature of the study and potential for later-emerging effects, the safety profile will be characterized for each sub-type over time. Supportive analyses will include evaluation using the PP population.

Subgroup analyses: analyses will be repeated among GM1 gangliosidosis patients and among GM2 gangliosidosis patients, and among the infantile and juvenile forms of both GM1 and GM2 gangliosidosis.

18.4 Missing data. Despite best efforts to avoid missing data, it is possible that some will occur and will be a potential limitation to the interpretation and generalizability of results. In particular, missing data may arise for non-survival outcomes (e.g. neurocognitive function data) in the event of death. For these instances, it is unclear whether a complete-case analysis (i.e. excluding patients who die) would be unbiased, and therefore would be unsatisfactory. It is also unclear what would be an appropriate magnitude of discount to satisfactorily represent the negative outcome of death. By conducting both the complete-case analysis (unbiased if death is independent of the non-survival outcome) and an analysis with an imputed value for instances of death (intention-to-treat type of analysis), the potential magnitude of treatment effect will be better characterized.

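### The exchangeable-GEE slope gives most weight to the children followed longest, so it is too flat if faster decliners within a sub-type die or miss visits; a random-slope mixed model on all observed scores should be the main analysis

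*Combined protocol and SAP*

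**What the plan says.** Section 18.3 defines the endpoint: "A secondary endpoint will be the rate of change (i.e., slope) in neurocognitive functioning over the duration of follow-up", to be set against natural history data. The estimator is given as "Using general estimating equations (GEE) and an exchangeable working correlation structure", with the same text in the Synopsis and sections 12.2 and 13.1. GEE is presented only as a way to obtain intervals and p-values that allow for repeated measurements. No random slope, weighting or joint model with death is named, and the plan does not say over which children, or what period, the slope is averaged.

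Section 18.3 also states "All analyses will be conducted separately for the two disease sub-types". Section 13.3 gives "A total of 30 infants or children" in six strata of five, so about 15 children per sub-type.

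The schedule in section 17.0 places testing at baseline, Year 1 and the annual visits of Years 2-5, at most six per child. Section 18.2 speaks of "correlation between baseline and annual follow-up for up to 4 years", which would be five. Section 17.0 adds that "due to disease progression or concurrent illness, some patients after enrollment may not be able to fulfill the annual visit requirement", and that these children stay in the study.

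For death, section 18.4 (repeated in 22.1) plans both a complete-case analysis, which it doubts itself, and an analysis with an imputed value that is not stated. Loss to follow-up is handled by LOCF, with sensitivity analyses and possibly multiple imputation.

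**The concern.** A single common slope fitted to children with different numbers of tests is a weighted average of the children's own slopes. Exchangeable GEE gives most of the weight to those tested longest. That is harmless if length of follow-up has nothing to do with rate of decline. If the children who decline fastest contribute fewest tests, the average is pulled towards the slow progressors.

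This concerns the point estimate, so a better variance estimator does not help. In a single-arm study whose slope is judged against external natural history, a decline that is too shallow points in the same direction as a treatment effect.

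**Working it through.** **1. Weights (arithmetic from the schedule).** With n annual tests, the spread of a child's test times is Sxx = n(n² - 1)/12.

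| Tests | 1 | 2 | 3 | 4 | 5 | 6 |
|---|---|---|---|---|---|---|
| Sxx | 0 | 0.5 | 2 | 5 | 10 | 17.5 |

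Six tests against two: 17.5/0.5 = 35. If follow-up stops at four years (five tests), 10/0.5 = 20.

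**2. Example that can be checked by hand.** Take five children with slope -1 and six tests, five with slope -5 and two tests, and a common intercept. The simple mean slope is -3. Weighting by Sxx gives (17.5 × -1 + 0.5 × -5)/(17.5 + 0.5) = -20/18 = -1.11. A GEE fit with exchangeable correlation 0.95 gives -1.10, with 0.5 it gives -1.03, and with independence -0.83. When all ten children have six tests, every version gives -3.0.

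**3. Simulation on observed scores.** The plan gives no slope, SD, correlation or dropout rate (section 18.2: "The sample size for the study was determined primarily by feasibility due to the extremely rare nature of the disease"), so it has no figure to reproduce and every input here is assumed. Inputs: 15 children, up to six annual tests, linear decline from a baseline of 40 months, mean slope -3 age-equivalent months per year, SD of slopes 2, SD of intercepts 6, residual SD 1.5, and dropout hazard 0.2 per year at the mean slope. The log hazard rises by g per SD of faster decline.

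| g | Exchangeable GEE | Independence GEE | Random-slope model (known variances) | Mean of per-child slopes |
|---|---|---|---|---|
| 0 | -3.01 | -3.00 | -3.01 | -3.02 |
| 0.5 | -2.33 | -2.21 | -2.69 | -2.80 |
| 1.0 | -1.89 | -1.74 | -2.37 | -2.53 |
| 1.5 | -1.65 | -1.51 | -2.11 | -2.28 |

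At g = 1.0, the 39% of children with six tests hold 83% of the Sxx weight. There the mixed model removes (2.37 - 1.89)/(3.00 - 1.89) = 0.48/1.11, about 43% of the GEE bias. Both conditions are needed: with no difference in slopes between children, GEE gives -3.00. With rolling entry and g = 0 it gives -3.03. With slope SD 1 and g = 1.0 it gives -2.46.

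A second set of assumptions (truth -4, slope SD 2-3, log hazard 0.5-1 per SD) gave -3.3 to -2.0 for GEE and -3.6 to -3.0 for the random-slope model.

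**4. The section 18.4 rules, same assumptions as step 3 (truth -3).**

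| Rule applied to all dropout | g = 0 | g = 1.0 |
|---|---|---|
| Children who die excluded | -3.04 | -1.67 |
| LOCF | -1.69 | -1.12 |
| Death scored 0 (assumed value) | -6.08 | -5.26 |

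In these runs each retained child has six values, so GEE and the per-child mean coincide and the distortion comes from the rule. The plan does not guarantee such balance. The Synopsis has rolling enrolment over five years in a five-year study, and children who miss visits are not clearly lost to follow-up. With rolling entry (1-5 years available) and children who die excluded, GEE gave -2.26 at g = 0.5 and -1.79 at g = 1.0, against -2.52 and -2.11 for the per-child mean. The weighting effect then adds to the survivor effect.

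**5. Score floor.** With an assumed baseline of 6 months, floor 0.5 and g = 1.0, full data give -0.84, observed-data GEE -0.82, and the per-child mean -1.47. At g = 0, observed-data GEE gives -0.96 against -0.83 for full data.

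**The case against.** The strongest reply is that the flattening is not established. Section 17.0 says only that some children may be unable to attend, and names concurrent illness beside progression. The contrast between rapid and slower decline in section 1.1 is between infantile and juvenile forms, which are analysed separately. Section 18.4 also has rules for death and loss to follow-up, and once visits are equal the choice of estimator no longer matters. This stands to the extent that the bias is conditional. It does not remove the point: each sub-type still pools Tay-Sachs, Sandhoff and GM1 disease, enrols from age 0 to 17 and admits children already treated, and the planned rules leave follow-up unequal.

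A reader might infer more than the documents support:

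- **That the slope will certainly be too flat.** Unequal follow-up from rolling entry alone causes no bias when decline is linear. Near a floor the direction is not assured, and a low death score makes the slope steeper.
- **That the exchangeable structure is to blame.** Independence GEE is flatter still.
- **That GEE is generally less precise.** With tests spread evenly over two to six and slope SD 2, the variance ratio of GEE to the per-child mean is 1.41 at residual SD 1.5, but 0.92 at 3 and 0.71 at 4.
- **That weighting children equally is the answer.** Step 5 shows it much too steep at a floor, and children with one test drop out.
- **That a false claim of benefit follows.** The documents give no natural-history slope, and section 1.1.3 calls those data limited and survey-based. A comparator weighted towards survivors could share the bias.

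**Conclusion.** The point holds in conditional form. The 35-to-1 weighting follows from the schedule. A slope that is too flat follows only if slopes differ within a sub-type and faster decliners have shorter follow-up. The documents make both plausible and quantify neither. Under the assumed inputs of step 3, with such a link, the GEE slope loses 0.67 to 1.35 of a true 3.0 months per year (3.00 - 2.33 and 3.00 - 1.65), and the random-slope model loses 0.31 to 0.89 (3.00 - 2.69 and 3.00 - 2.11). These figures illustrate size and direction; they are not forecasts.

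Section 18.4 does not settle the matter, because its options bias in opposite directions and none is named as primary. This is a secondary endpoint, and the remedy is cheap enough to be worth adopting.

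**What to change.** In the Synopsis and sections 12.2, 13.1 and 18.3, make the main slope analysis a linear mixed model with a random intercept and a random slope per child. Fit it in each sub-type to all observed scores, including those before death, without LOCF and without excluding children who die.

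Keep the exchangeable GEE and the section 18.4 complete-case and imputed-death analyses as sensitivity analyses, and state the imputed death value in advance. Report the unweighted mean of per-child slopes as a further check, not as the main estimate. State that the mixed model removes only part of the bias if death depends on the unobserved slope. Plan a check of linearity and floor effects, because the behaviour of the mixed model near a floor is not quantified here. A joint slope-death model is optional: about 15 children per sub-type may not support one.

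The cost is SAP wording and a few lines of code. The drawbacks are wider intervals if slopes hardly differ between children, and possible non-convergence, so the SAP should name a fallback.

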If the dose of 100 mg three times daily is well tolerated (i.e., patient does not show signs of gastrointestinal side effects of diarrhea, reflux or gastrointestinal cramping), then the dose will continue at 100 mg three times daily.

If the subject's BSA is $> 1.3 \text{ m}^2$, and if their insurance covers up to 600 mg/day miglustat, if the dose of 100 mg three times daily is well tolerated for two weeks, then increase dose to 100 mg in the morning and at midday and 200 mg in the evening for two weeks. If this dose is well tolerated, then increase dose to 200 mg in the morning, 100 mg at midday and 200 mg in the evening for two weeks. If this dose is well tolerated, then increase dose to 200 mg in the morning, 200 mg at midday and 200 mg in the evening for two weeks. If the dose of 200 mg three times daily is well tolerated (i.e., patient does not show signs of gastrointestinal side effects of diarrhea, reflux or gastrointestinal cramping), then the dose will continue at 200 mg three times daily.

If the subject's BSA is $> 1.3 \text{ m}^2$, but the subject's insurance does not cover miglustat dose of 200 mg three times daily, subject will use maximum dose of miglustat that is covered by the subject's insurance, not to exceed 600 mg/day miglustat.

10.13 Dose adjustment guidelines:

Peripheral neuropathy: If a patient is found to have peripheral neuropathy that is increased above pre-treatment levels, the dose of miglustat will be reduced by one-third and patient will be reassessed by neurologist 1 month later. If peripheral neuropathy has not resolved, the miglustat dose will be reduced by another one-third and the patient evaluated again after 1 month. If peripheral neuropathy continues, at the discretion of the neurologist, miglustat may be stopped.

Thrombocytopenia: If a patient is found to have thrombocytopenia, the dosing of miglustat will be held and CBC with platelets and differential checked weekly until platelet count recovers. If platelet counts do not recover after 2 weeks, then at discretion of study physician, miglustat therapy may be stopped, if deemed necessary under clinical discretion of study physician.

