15.0 Laboratory Testing Procedures

All labs will be sent to Fairview Labs for in-house processing, or to be forwarded by Fairview Labs to outside processing facilities:

Fairview Diagnostic Laboratories
[name]
[name]
[name]
[contact] voice, [contact] fax

15.1 Other parameters being monitored. The following parameters will be monitored at baseline and then every 3 months for the first year of treatment, and then every 6 months thereafter: subject weight, height, occipital-frontal circumference, comprehensive metabolic panel (including serum creatinine and estimated GFR and liver function tests), CBC with platelets and differential, lipid panel, neurologic exam to assess for peripheral neuropathy, and urine pregnancy test in all post-pubertal females. It is acceptable for this interval safety monitoring to not occur at the primary study site as long as the neurologic exam could be performed by an experienced practitioner.

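### Section 18.3 tracks safety over time by AE counts and percentages with no exposure denominator per period; add rates per child-year by phase, with the number of checks done

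*Combined protocol and SAP*

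**What the plan says.** On safety, section 18.3 states: "Safety analyses will be primarily descriptive, reporting the number and percentage of AEs and descriptive summaries". It then adds: "Due to the longitudinal nature of the study and potential for later-emerging effects, the safety profile will be characterized for each sub-type over time". Section 18.1 defines the safety population by exposure to the regimen. No section defines time windows, child-years or a denominator per period.

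Scheduled observation changes along the time axis:

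- Sections 11.5 and 15.1 set labs, weight and other growth measures, and the neuropathy exam at baseline, then "every 3 months for the first year of treatment, and then every 6 months thereafter".
- Section 17.0 asks for at least weekly calls during diet transition and miglustat titration. On a stable dose, "side effects will be assessed by telephone contact or at clinic visits every 3 months throughout the study period".
- For miglustat tolerance and for the diet, section 17.0 says that after the first year "assessments will continue for a minimum of once monthly".

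Exposure changes too. The synopsis gives rolling enrolment over five years and a study duration of five years. Section 17.0 starts a child who already uses the regimen at the time-point matching the time already spent on it. Section 18.3 cites a natural-history median survival of 47 months for the infantile form and 14.5 years for the juvenile form.

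**The concern.** The over-time summary exists to show harm that appears late. A falling count in later periods can mean less harm, fewer children still observed, or fewer scheduled checks. The measures named in 18.3 do not separate these, and there is no control arm to show what the calendar and schedule alone would produce. A reader could then be reassured by a decline that reflects shrinking exposure. What is at stake is the reading of the descriptive safety table. No hypothesis test and no numerical stopping threshold depends on it.

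**Working it through.** The plan states no AE rate, exposure total or precision, so there is no figure to reproduce. The check asks how much the summary could move for reasons other than the true rate.

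**1. Child-years by study year.** Inputs: 15 children per sub-type (13.3: three diseases, five each) and five years of enrolment in a five-year study (synopsis). Assumed: even accrual over A years, a common close at year 5, no deaths. For A = 5, child-years per enrolled child in year k are 1 − (k − 0.5)/5.

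| Accrual | Y1 | Y2 | Y3 | Y4 | Y5 | Y5/Y1 |
|---|---|---|---|---|---|---|
| 1 year | 1.00 | 1.00 | 1.00 | 1.00 | 0.50 | 0.50 |
| 3 years | 1.00 | 1.00 | 0.83 | 0.50 | 0.17 | 0.17 |
| 5 years | 0.90 | 0.70 | 0.50 | 0.30 | 0.10 | 0.11 |

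If every child has five full years, the ratio is 1.0. At a constant 1 AE per child-year (assumed), 15 children with five-year accrual give 13.5, 10.5, 7.5, 4.5 and 1.5 AEs.

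**2. Adding deaths (infantile).**

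- Exponential survival with a 47-month median is memoryless. With all children followed for five years, Y5/Y1 = 2^(−48/47) = 0.49; with five-year accrual it is about 0.06 (15 children: 12.4, 8.1, 4.9, 2.4, 0.7 child-years).
- Taking median remaining survival as 47 − 24 = 23 months (entry at 24 months assumed) with five-year accrual gives 0.021/0.760 = 0.03.
- A rising hazard (Weibull shape 3, entry at 1 to 3 years) goes lower: 0.01 to 0.16 even if all are followed for five years.
- For juveniles, assumed entry at 6 to 14 years and shape 1 or 3 give 0.47 to 0.83 with all followed, and 0.05 to 0.09 with five-year accrual.

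**3. Can a real increase be hidden?** Take the memoryless case with five-year accrual, and let the true rate double from 1 to 2 after year 1. Expected counts are 12.4, 16.2, 9.7, 4.9 and 1.4. They rise in year 2 and sit below year 1 from year 3 on. Rates per child-year would read 1.0, then 2.0.

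**4. Percentages.** Five-year accrual, no deaths, constant rate of 1, denominator = children entering that year. A full year gives 1 − e^(−1) = 0.632. A part year, uniform on 0 to 1, gives 1 − 0.632 = 0.368.

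- Year 1: 0.8 × 0.632 + 0.2 × 0.368 = 0.579.
- Year 5 (part years only): 0.368. Ratio 0.368/0.579 = 0.64.
- If the rate has doubled, year 5 gives 1 − (1 − e^(−2))/2 = 0.568, close to year 1's 0.579. Year 2 would show 0.75 × 0.865 + 0.25 × 0.568 = 0.79, so the rise would be visible early and then fade.
- If the denominator is instead all 15 children, year 5 gives 0.2 × 0.368 = 0.074 and a ratio of 0.074/0.579 = 0.13. The plan does not say which denominator applies.

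**5. Scheduled checks.** Labs and exams go from 4 to 2 a year, so intervals are 91.3 and 182.6 days. By scheduled checks alone, the chance of meeting an abnormality is min(1, duration/interval).

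| Duration | Year 1 | Later |
|---|---|---|
| 30 days | 0.33 | 0.16 |
| 60 days | 0.66 | 0.33 |
| 90 days | 0.99 | 0.49 |
| 180 days | 1.00 | 0.99 |

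An abnormality lasting six months or more is met in both periods, on average 46 and 91 days after onset (half the interval). These are upper bounds on the loss, since other routes of detection are ignored. Dividing by child-years leaves the halving in place.

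**The case against.** The strongest reply is that the plan promises percentages and descriptive summaries as well as counts, and nothing in it rules out exposure-adjusted rates. This partly stands. A percentage of children entering each period removes most of the count distortion (0.64 against 0.11 in the same scenario). But 18.3 neither chooses that denominator nor calls for rates, and even that percentage can look level across years 1 and 5 after a doubling.

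The size is also driven by assumption, and this stands in full. The 0.03 end uses an ad hoc remaining survival. The 47 months refers to infantile GM2 (12.1), while 5 of the 15 infantile children have GM1. No scenario includes children already on the regimen, who add child-years to later periods and take them from year 1.

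A reader might infer that safety surveillance as a whole thins out after year 1. The documents do not support that. Symptom contact goes from quarterly on a stable dose in year 1 to at least monthly later. Section 19.1 has investigators identify AEs as they occur. Weekly calls resume "any time the dose is decreased due to adverse events, until symptoms have re-solved". Section 10.13 requires "CBC with platelets and differential checked weekly until platelet count recovers" in thrombocytopenia, and for worsened neuropathy "patient will be reassessed by neurologist 1 month later". The thinning concerns scheduled lab, weight and neuropathy checks, and bites on short-lived findings not otherwise noticed. For parent-reported symptoms, the documents fix neither the direction nor the size of any shift.

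Finally, late-phase rates will be imprecise: 3 events in 2 child-years is 1.5 per child-year, exact 95% interval 0.31 to 4.38. That is true, and is a reason to print the child-years and interval, which a bare count hides.

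**Conclusion.** The point holds as a worthwhile, inexpensive improvement. Section 18.3 sets out to detect late effects but names measures that mix the true rate with changing exposure, and no other section supplies the denominator. Year-5 to year-1 child-years could lie anywhere from about 0.03 to 1.0 under the assumptions shown. Steeper survival curves go below that range, and entry of prior users pushes the ratio up. A decline in counts is therefore possible and plausible under rolling entry in a fatal disease, but not certain, and no single ratio should be quoted as the expected bias.

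The halved lab and exam checks are a separate problem, worth up to a factor of two for abnormalities lasting about three months or less. It would be tempting to say that rates per child-year cure both; they cure only the first. Nor do the documents support reading this as a flaw in a stopping rule: 21.1 mentions a rate of severe AEs but sets no threshold tied to these tables.

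**What to change.** In 18.3, add a table by sub-type and time-on-regimen phase: diet transition and titration, rest of year 1, year 2 onward. In each cell give AE events, child-years under study observation, the rate per child-year and an exact 95% interval. Assign phase by each child's actual time on the regimen, so that children who join part-way contribute only to the phases in which they were observed.

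Beside the rates, show the number of scheduled lab/exam checks done in each phase. Present lab/exam-detected events separately from reported symptoms, and state that comparing the former between phases is limited by check frequency. The CTCAE classification in 19.2 can support this split. Keep the planned counts and percentages as overall totals.

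Cost: a longer table, with sparse and imprecise cells in about 15 children per sub-type. No visits or contacts are added and no events are discarded.
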